The frequency and percentage of subjects who report treatment-emergent adverse events (TEAEs), serious TEAEs, and TEAEs leading to premature discontinuation of study will be summarized. An AE is treatment emergent if 1) it occurs after the first dose of study treatment; or 2) exists before the first dose of study treatment and its severity worsens or frequency increases after first dose. The AEs will be coded using the MedDRA preferred term and system organ class and listed by severity and the causal relationship with the study drug. The AEs leading to discontinuation of the study will be listed. No hypothesis test will be performed. Separate analyses will be performed for ocular specific and all AEs (including systemic). Other safety endpoints including visual acuity, slit-lamp biomicroscopy, fundus color photography, and intraocular pressure will be summarized by treatment group and visit using descriptive statistics. Changes or shifts from baseline will also be summarized where appropriate. For assessments performed on eyes, the data for study eye and fellow eye will be summarized separately. In addition, shifts from baseline to worst on-treatment value for ocular safety assessments will be summarized.

Data Monitoring and Clinical Endpoint Committee

Not applicable

Table of Contents

LIST OF TABLES	8
LIST OF FIGURES	8
LIST OF APPENDICES	8
LIST OF ABBREVIATIONS AND DEFINITIONS OF TERMS	9
1 INTRODUCTION	11
1.1 Medical Background	11
1.2 Overview of Drug	11
1.3 Non-clinical Studies	12
1.4 Previous Clinical Studies	12
1.4.1 Phase I Study	12
1.4.2 Phase II Study	13
1.5 Rationale	14
1.6 Clinical Risk/Benefits Assessment	15
2 OBJECTIVE	17
2.1 Primary Objective	17
2.2 Secondary Objective	17
3 STUDY ENDPOINTS	18
3.1 Primary Efficacy Endpoint	18
3.2 Secondary Efficacy Endpoints	18
3.3 Safety Evaluation	18
4 INVESTIGATIONAL PLAN	20
4.1 Overall Study Design and Plan	20
4.2 Rationale of Study Design	22
4.3 Rationale of Dose/Regimen and Duration of Treatment	22
5 SELECTION OF STUDY POPULATION AND WITHDRAWAL CRITERIA	23
5.1 Inclusion Criteria	23
5.2 Exclusion Criteria	24
5.3 Subject Identification	26
5.4 Previous, Concomitant and Prohibited Medications	26
5.4.1 Other Medications for the Treatment of Dry Eye	26
5.4.2 Prohibited Medications	26
5.4.3 Other Prohibited Medications	26
5.5 Other Restrictions, Illicit Drugs or Drug Abuse	26
5.5.1 Illicit Drugs	26
5.5.2 Dietary Restriction	26
5.6 Reasons for Discontinuation of Treatment or Study Withdrawal	27

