7.2.4 Causality

The relationship of each AE to the administration of study drug will be assessed by the Investigator after careful consideration, and according to the following guidelines:

Definitely: A reaction that follows a reasonable temporal sequence from administration of study drug; that follows a known or expected response pattern to the study drug; it disappears or decreases on cessation or reduction in study drug dose; and/or it reappears or worsens when the study drug is administered;

Probably: A reaction that follows a reasonable temporal sequence from administration of study drug; that follows a known or expected response pattern to the study drug; but it could also be reasonably explained by other factors such as underlying disease, complications, concomitant medications or treatments;

Possibly unrelated: A reaction that does not follow a reasonable temporal sequence from administration of study drug; that does not follow a known or expected response pattern to the study drug; it could be reasonably explained by other factors such as underlying disease, complications, concomitant medications or treatments;

Unrelated: A reaction that follows a reasonable temporal sequence from administration of study drug; that follows a known or expected response pattern to the study drug; it disappears or decreases on cessation or reduction in study drug dose; and/or it reappears or worsens when the study drug is administered;

Inaccessible: A reaction for which current data is too insufficient to assess its relationship with the study drug.

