9.5.2 Safety Analysis

Frequencies and percentages of subjects with treatment-emergent adverse events (TEAEs), serious TEAEs, and TEAEs causing premature discontinuation will be provided by treatment group. An AE is treatment emergent if it 1) occurs after the first dose of randomized study treatment or 2) if it is present prior to receipt of randomized study treatment but worsens in severity or increases in frequency after the first dose of randomized study treatment. Frequencies and percentages of subjects with AEs, SAEs, and AEs causing premature discontinuation will be provided by treatment group. The AEs will be listed by MedDRA SOCs and PTs and the AE listings will be categorized by severity, the causal relationship with study drug, and whether the AEs leading to discontinuation of study. No hypothesis test will be performed. Separate analyses will be performed for ocular specific and all AEs (including systemic).

Other safety endpoints including visual acuity, slit-lamp biomicroscopy, fundus color photography, drop tolerance, and intraocular pressure, will be summarized by treatment group and visit using descriptive statistics. Changes from baseline will also be summarized where appropriate. For assessments performed by eye, study eye and fellow eye will be summarized separately. In addition, shifts from baseline to worst on-treatment value will be summarized.

The exposure time (number of days) and drug administration times will be summarized by treatment group. The number and percentage of subjects with compliance will be calculated. The total exposure of the safety population will be summarized based on actual treatment received.

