7.1 Adverse Event

An overall summary will be presented that includes the number of AEs, serious AEs (SAE), TEAEs and serious TEAEs (TE-SAE). The summary will also include the number and percentage of subjects withdrawn due to an AE, the number and percentage of subjects with an AE resulting in death, and the number and percentage of subjects who experienced at least one TEAE, SAE and TE-SAE, by treatment group and for all subjects. This summary will include breakdowns of AEs further categorized as ocular or non-ocular. The summary will also include the number and percentage of resolved ocular AEs, and the mean number of days until AE resolution for resolved ocular AEs. AEs recorded in the eCRF which began prior to treatment will not be included in the summary tables but will be included in the AE data listings. All AEs will be coded using MedDRA Version 22.

Treatment-emergent adverse events (TEAEs) are defined as any adverse event that occurs or worsens from the first dose of study treatment (at visit 2) to last dose+7 day. Additional summaries of TEAEs will be provided showing the number and percentage of subjects who experienced at least one TEAE. These summaries will be presented by SOC and PT. Non-ocular TEAEs will be summarized using discrete summary statistics and presented by treatment group at the subject level by SOC and PT. Ocular TEAEs will also be

similarly summarized at the subject level. If a subject reports the same PT multiple times within the same SOC, that PT will only be reported once within that SOC. In the summary, SOC will be listed in order of descending frequency by study active treatment for all subjects; PTs will be listed in order of descending frequency for all subjects within each SOC. The occurrence of non-ocular and ocular TEAEs will also be tabulated by SOC, PT, and maximal severity.

Separate summaries will be provided for the following categories of AEs:

- Ocular TEAEs
- Non-ocular TEAEs
- Treatment-related ocular TEAEs
- Treatment-related non-ocular TEAEs
- SAEs

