Severity of an adverse event is defined as a qualitative assessment of the degree of intensity of an adverse event as determined by the investigator or reported to him/her by the patient/subject. Summaries of TEAEs by maximal severity will be presented for ocular AEs and non-ocular AEs separately. The number of subjects with any TEAEs (along with percentages) will be tabulated by SOC and PT within each SOC by treatment group. To count the number of subjects with any TEAEs, if a subject has multiple TEAEs coded to the same PT within the same SOC, the subject will be counted once under the maximal severity. All probable, unclassified, and definite TEAEs are considered as treatment-related TEAEs. All AEs will be presented in a subject listing.

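### Protocol 7.2.4 defines the causality category Unrelated in the same words as Definitely, so the written criteria cannot separate the two ends of the scale behind the treatment-related TEAE tables

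*Protocol*

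**What the plan says.** Protocol 7.2.4 directs the investigator to assess every adverse event against five categories: *Definitely*, *Probably*, *Possibly unrelated*, *Unrelated* and *Inaccessible*. The highest begins "Definitely: A reaction that follows a reasonable temporal sequence from administration of study drug; that follows a known or expected response pattern". The fourth begins "Unrelated: A reaction that follows a reasonable temporal sequence from administration of study drug; that follows a known or expected response pattern". Between them stands a category built on the negated criteria: "Possibly unrelated: A reaction that does not follow a reasonable temporal sequence from administration of study drug; that does not follow a known".

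SAP 7.1 turns these categories into a two-way split: "All probable, unclassified, and definite TEAEs are considered as treatment-related TEAEs". It plans separate tables for "Treatment-related ocular TEAEs" and "Treatment-related non-ocular TEAEs". Protocol 9.5.2 adds that "the AE listings will be categorized by severity, the causal relationship with study drug", and the protocol synopsis says much the same. The SAP gives no causality definitions of its own, so Protocol 7.2.4 is the only source.

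**The concern.** A causality scale should run in one direction, from clearly drug-caused to clearly not. This one runs downward as far as *Possibly unrelated* and then returns, at *Unrelated*, to the criteria for the top category. An investigator who follows the text can put an event with plausible timing, a known pattern and a positive dechallenge or rechallenge into either of two categories. One is counted as treatment-related and the other is not.

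The outputs at stake are the treatment-related ocular and non-ocular TEAE summaries and the causality entry in the AE listings. Safety is the secondary objective (Protocol 2.2). SAP 1.4 names safety data as an input to the Phase 3 decision when the observed difference falls between -0.3 and -0.1. The protocol also presents earlier experience by this measure: in the US Phase II study (Protocol 1.4.2), 16 subjects (10.7%) had a related ocular TEAE, of whom 7 were on 0.10%, 8 on 0.25% and 1 on placebo. If counts here are similarly small, with 50 subjects planned per group, a few misplaced events would be visible in the table.

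**Working it through.** There is no stated figure to reproduce; the check is on text and logic.

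**Step 1: compare the definitions.** The full text after the *Definitely* label and the full text after the *Unrelated* label were compared as strings. They match exactly, at 48 words each. Both sentences are complete, so this is not a redaction or a broken table.

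**Step 2: reduce each definition to its criteria.** Four yes/no attributes are enough: plausible timing (T), known response pattern (K), another reasonable explanation (O), and positive dechallenge or rechallenge (D). The criteria within a category are read jointly, and an attribute that a category does not mention is left free. Four attributes give 2 × 2 × 2 × 2 = 16 profiles.

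| Category | Required | Profiles met | Treated as related by SAP 7.1 |
|---|---|---|---|
| Definitely | T yes, K yes, D yes | 2 (O free) | yes |
| Probably | T yes, K yes, O yes | 2 (D free) | yes |
| Possibly unrelated | T no, K no, O yes | 2 (D free) | no |
| Unrelated, as written | T yes, K yes, D yes | 2 (O free) | no |

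*Inaccessible* is for events with too little information and has no profile.

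**Step 3: look at the overlaps.**

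- *Definitely* and *Probably* share one profile (all four attributes yes), so together they cover 2 + 2 − 1 = 3. Both count as related, so this overlap does not affect the tables.
- *Unrelated* and *Definitely* share 2 of 2 profiles. No profile meets *Unrelated* alone.
- *Unrelated* and *Possibly unrelated* share 0 profiles, although they are neighbours on the scale.
- Of the 3 profiles that meet *Definitely* or *Probably*, 2 also meet *Unrelated*.

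**Step 4: trace what depends on the category.**

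- *Affected:* the two treatment-related TEAE summaries (SAP 7.1), the causality field in the listings (protocol synopsis and 9.5.2), and the causality that must accompany an initial SAE report (Protocol 7.2.7.1). Some reporting also turns on the causality judgement: SAEs between the last visit and study completion, post-study events (both in Protocol 7.2.2), and expedited reports of suspected reactions (Protocol 7.2.7.4).
- *Not affected:* the all-causality TEAE tables, whether an event is listed at all, the 24-hour notification of SAEs during the study (Protocol 7.2.2, 7.2.3 and 7.2.7.1), the collection of SAEs for 7 days after the last dose whatever their cause (Protocol 8.3 and 8.4), and the efficacy analyses.

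**The case against.** The strongest reply is that this is an evident copying slip in a scale whose labels explain themselves. The SAP sorts events by label, not by the text of the definition, so an error reaches a table only if an investigator picks *Unrelated* for an event believed to be drug-caused. The tables concerned are descriptive, and no hypothesis test is planned on them. That stands, and it limits the severity. It does not make the text right: the protocol tells investigators at several sites to apply these definitions, and no data monitoring or endpoint committee stands behind them.

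The profile count can be called a construct. The choice of four attributes and the joint reading of clauses linked by and/or are assumptions, and 2 of 16 is not a frequency of events. That is fair; the count only shows how complete the overlap is.

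The US Phase II figures come from another study whose causality scale the documents do not give. They show that relatedness is a measure the sponsor reports, not that this wording would have changed it. That also stands.

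Finally, a replacement that only keeps out *Definitely* and *Probably* events could still duplicate *Possibly unrelated*. On the same enumeration, 11 of 16 profiles (16 − 3 − 2) meet no category, among them all 4 with plausible timing but no known pattern. Both points bear on how the replacement is drafted; neither removes the error.

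**Conclusion.** The concern holds. As written, Protocol 7.2.4 cannot distinguish its *Definitely* category from *Unrelated*, while SAP 7.1 places the two on opposite sides of the treatment-related split. The overlap is total: every profile that meets one meets the other.

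The effect on the reported counts is unknown and probably small, because most investigators will go by the label. This assumes that the eCRF carries no guidance repeating the faulty text; the documents do not show the eCRF. The point should be fixed, but it does not threaten the trial's main conclusions.

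**What to change.** - **Protocol 7.2.4.** Replace the text under *Unrelated* with a definition that meets two conditions: none of the 3 profiles that satisfy *Definitely* or *Probably* may satisfy it (2 do now), and it must ask for more evidence against a drug cause than *Possibly unrelated* does. Repeating the *Possibly unrelated* text would pass the first condition and fail the second. The redraft is also the time to decide where events with plausible timing but no known pattern belong.
- **eCRF guidance.** Confirm that any completion guidance carries the corrected text.
- **Events already coded *Unrelated*.** Re-check them against the new definition while treatment is still blinded. If the blind no longer holds, which the documents do not settle, the re-check should be done by people without access to the assignments, and the report should say so.
- **SAP 7.1.** The SAP counts unclassified events as related, but the protocol has no category of that name. State that it corresponds to *Inaccessible*, if that is what is meant.

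The cost is one corrected definition, one clarifying phrase in the SAP and a limited blinded re-check. Because the protocol text changes, ethics committee review and approval apply as set out in Protocol 10.2. No patients, visits or procedures are added.

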7.2.5 Recording of Symptoms, Signs and Scale/Questionnaire Evaluation Results

During the study period, not all symptoms, signs, and scale/questionnaire assessment will be recorded as AEs, and the following conditions will not be recorded as AEs:

- Symptoms and signs due to fluctuation in dry eye disease. Symptoms and signs of dry eye disease will be analyzed as the efficacy endpoint and will not be recorded as AEs;
- The assessment of tolerance to eye drops will be analyzed as a safety endpoint, and will not be recorded as AEs;
- The CAE simulates daily adverse environment and triggers the symptoms and signs which will be evaluated as the efficacy endpoint. Therefore, dry eye symptoms and signs triggered by CAE will not be recorded as AEs unless the dry eye symptoms and signs triggered by CAE exceed the expected range of dry eye.

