1.4 Previous Clinical Studies

1.4.1 Phase I Study

A first-in-human study was completed in Korea in August 2016 aiming to assess the safety, local tolerance, and PK properties of HBM9036. A total of 77 subjects were screened and 20 subjects were randomized to Group A and Group B to receive topical ophthalmic instillation of HBM9036 0.5 mg/mL and 5 mg/mL twice in one day into left eyes, while right eyes received vehicle placebo.

Of the 20 subjects who received study drugs, 11 subjects reported 27 AEs. Twenty AEs were mild in severity and the subjects recovered without sequela. The remaining 7 AEs were moderate in severity, and all events were reported by one subject. Among the 7 moderate AEs, all symptoms except for corneal opacity resolved completely. The assessment of causal relationship between the study drug and the 7 AEs was determined to be “unlikely” for all events. The most frequently reported AE after administration of the study drug was conjunctival hyperemia, with 18 events reported. There were 5 AEs reported by 2 subjects from the HBM9036 0.5 mg/mL group and 6 AEs reported by 3 subjects from the HBM9036 5 mg/mL group. The remaining 7 AEs were reported by 3 subjects in the placebo group. There were 24 AEs reported by 9 subjects (45%) that may have been caused by the study drug (the causal relationship was possible, probable, or certain). Among the AEs thought to be caused by the study drug in each group, conjunctival hyperemia was the most frequently reported (17 AEs reported by 7 [35.0%] subjects). All conjunctival hyperemia events were mild, and the subjects recovered without sequelae. There was no serious AE or unexpected adverse drug reaction reported, and no clinically significant changes were observed in vital signs, physical examinations, and medical laboratory tests. Local tolerance was assessed and there were no moderate or severe ophthalmologic symptoms observed.

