1.4.2 Phase II Study

The Phase II, dose range, and proof-of-concept study of HBM 9036 was completed in the US. This was a multicenter, randomized, double-blinded, placebo-controlled study. Subjects were randomly assigned to one of three treatment groups (HBM9036 Ophthalmic Solution 0.10%, 0.25% or placebo) to receive topical ophthalmic drops administered bilaterally BID. The study lasted for 8 weeks and included 6 visits. Although the primary sign of fluorescein staining at Visit 6 pre-CAE was not met with an ANCOVA analysis, analysis of the change in fluorescein staining score pre-CAE to post-CAE as well as post-CAE showed significant treatment differences from baseline starting as early as Visit 4 (Day 15) in total corneal and superior staining, and these significant treatment differences became consistent at Visit 5 (Day 29) and Visit 6 (Day 57). Significant improvements in burning and itching as assessed by the VAS were seen in favor of the HBM9036 0.25% group as early as Visit 4 (Day 15) and continued to Visit 6 (Day 57). Significant improvement was observed in total OSDI score in the HBM9036 0.25% treatment group compared with placebo group.

In the safety population, 44 (29.3%) subjects reported 64 AEs. Of them, 37 (24.7%) subjects reported 51 treatment-emergent adverse events (TEAEs), including 26 ocular TEAEs and 25 non-ocular TEAEs. All TEAEs were of mild or moderate severity. A total of 16 (10.7%) subjects reported at least one ocular TEAE related to the study drug. Of them 7 subjects were treated with HBM9036 (HL036) 0.10%, 8 subjects were treated with HBM9036 0.25%, and 1 subject was treated with placebo. The most common unexpected ocular TEAEs related to the study drug were installation site pain and allergic conjunctivitis. No deaths or SAEs were reported in the study. A total of 8 subjects withdrew from the study due to allergic conjunctivitis: 3 subjects were from HBM9036 (HL036) 0.10% group and 5 subjects were from HBM9036 (HL036) 0.25% group. No change of clinical significance was reported for other safety endpoints.

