7.2 Adverse events

7.2.1 Definition of AEs

An AE refers to all untoward medical occurrence after the use of an IP. An AE can be any sign, symptom or abnormal clinical laboratory results, but may not necessarily have a causal relationship with the IP.

An AE includes, but are not limited to:

- Any symptom or condition (medical history) not reported previously by subjects;
- An aggravation of existing symptoms or conditions;
- Significantly increased frequency or intensity of existing events or conditions;
- Conditions discovered or diagnosed for first time after the administration of the investigational product, even if they may already exist prior to initiation of the study.

An AE does not include:

- Routine medical or surgical procedures caused by non-disease factors (e.g., plastic surgery, endoscopy, biopsy);
- Planned surgical procedures before enrollment (e.g., cataract surgery) or hospitalization due to social factors (e.g., medical insurance);

- Overdose of either study drug or concurrent medication without any clinical signs or symptoms;
- Non-clinically significant abnormal laboratory values. (If accompanied by signs/symptoms, the signs or symptoms are considered an AE.).

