7.2 Other Safety Endpoints

Best-Corrected Visual Acuity (ETDRS)

The observed and change from baseline visual acuity will be summarized for each eye (study eye and fellow eye) using continuous descriptive statistics by visit for each treatment group.

Slit-Lamp Biomicroscopy Examination

The results will be summarized using counts and percentages for each treatment group at each visit for each eye (study eye and fellow eye). Percentages will be based on the number of subjects in each treatment group with responses. Shift tables for the slit-lamp biomicroscopy parameters will also be provided comparing each follow-up visit to baseline.

Ora Calibra[®] Drop Comfort Assessment

Drop Comfort Questionnaire responses will be summarized by treatment group using qualitative summary statistics. Subjects with at least one negative response will also be

summarized by treatment group. Analyses will be performed on the SS.

Intraocular Pressure (IOP)

The IOP values and changes from baseline for each eye (study eye and fellow eye) will be summarized using continuous descriptive statistics by visit and eye for each treatment group and for all actively treated subjects.

Fundus photography/dilated fundoscopy

The following examinations are done in the study:

- Vitreous
- Retina
- Macula
- Choroid
- Optic Nerve

The results will be summarized using counts and percentages for each treatment group at each visit for each eye (study eye and fellow eye). Percentages will be based on the number of subjects in each treatment group with responses.

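### Protocol 7.2.5 excludes dry-eye signs and symptoms and drop-tolerance results from AE recording with no limit for worsening, in conflict with 7.2.1, so some ocular reactions may be under-recorded

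*Protocol*

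**What the plan says.** Protocol 7.2.5 states that not every symptom, sign or scale result becomes an AE, and gives three exclusions:

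1. Dry eye. The bullet opens with "Symptoms and signs due to fluctuation in dry eye disease" and then adds, without that qualifier, "Symptoms and signs of dry eye disease will be analyzed as the efficacy endpoint and will not be recorded as AEs".
2. Drop tolerance: "The assessment of tolerance to eye drops will be analyzed as a safety endpoint, and will not be recorded as AEs".
3. Findings provoked by the CAE. These are also excluded, but "unless the dry eye symptoms and signs triggered by CAE exceed the expected range of dry eye".

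The AE definition in Protocol 7.2.1 includes previously unreported symptoms, aggravation of existing ones, and "Significantly increased frequency or intensity of existing events or conditions". The treatment-emergent definitions in Protocol 9.5.2 and SAP 7.1 include worsening after the first dose, but they act only on events already recorded as AEs.

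Drop tolerance is assessed only at Visit 2 (Protocol 7.1.3). Section 8.1.3 collects a scale immediately after the first dose and at 1 and 2 minutes, and a questionnaire at 3 minutes. SAP 7.2 specifies an analysis for the questionnaire alone: "Drop Comfort Questionnaire responses will be summarized by treatment group using qualitative summary statistics". Protocol 9.5.2 asks for drop tolerance to be summarized by group and visit.

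On earlier experience, Protocol 1.4.1 names conjunctival hyperemia as the most frequent related event in Phase I. For the US study, 1.4.2 says: "The most common unexpected ocular TEAEs related to the study drug were installation site pain and allergic conjunctivitis".

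**The concern.** Two of the three exclusions have no point at which worsening turns into an event, while the general definition says that worsening is an event. One site may treat 7.2.5 as the specific rule and only score the finding; another may follow 7.2.1 and report it. Both could defend their choice from the protocol.

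This matters because a local reaction to the drop can look like the disease under study. Safety is the secondary objective (2.2), the trial is meant to inform Phase III (2.1), and there is no data monitoring committee (7.2.11). The ocular treatment-emergent tables are where a reader will look for local reactions. An under-count there could understate a difference between arms.

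**Working it through.** **Step 1: how the two sections treat each finding.**

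| Finding | Already scored as | Under 7.2.1 | Under 7.2.5 |
|---|---|---|---|
| Worsening conjunctival redness | Entry criterion 9 (score of at least 1 in the study eye) and secondary endpoint | AE if aggravated | Excluded by the second sentence of bullet 1; open if the first sentence restricts it to fluctuation |
| Worsening burning/stinging or itching | VAS items (Appendix 1); burning is also a diary endpoint | AE if aggravated | Same as above |
| Pain at the first dose | Visit 2 tolerance assessment; pain is also a VAS item | AE if new or worse | The tolerance result is excluded by bullet 2 |
| Pain at later doses | VAS item | AE if new or worse | Not covered by bullet 2 |
| Diagnosed allergic conjunctivitis | Not a dry-eye measure | AE | Not excluded |

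The conflict is confined to the first three rows, with some doubt over the fourth.

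**Step 2: whether other data replace an AE record.**

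- *Efficacy summaries.* SAP 6.3 analyzes the secondary endpoints on the per-protocol set with observed data only. The scores carry no causality or AE severity grade, and the redness endpoint concerns the study eye. Protocol 9.1 requires completion for the per-protocol set (SAP 2.3 does not repeat this). The end-of-treatment column of Protocol Table 1 schedules no redness, discomfort or VAS score.
- *Slit lamp.* It is done at every visit, and SAP 7.2 reports both eyes with shift tables. Findings are graded Normal or Abnormal, with a flag for clinical significance (Appendix 1). An eye already Abnormal at baseline cannot show worsening on the two-level grade, and the SAP does not say that the shift tables use the flag.
- *Withdrawal reasons.* These are summarized (SAP 3.1), but lack of efficacy is one of the listed reasons (Protocol 8.6), so a reaction taken for worsening disease could be filed there.

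Cover is therefore partial.

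**Step 3: what the earlier studies say about size.** The protocol's own percentages reproduce:

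- Phase I: 7/20 = 35.0% with related hyperemia.
- US Phase II: 44/150 = 29.3%, 37/150 = 24.7%, 16/150 = 10.7%. The 150 is implied by these percentages and is not stated in 1.4.2.

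Phase I hyperemia: 5 + 6 + 7 = 18 events. On active drug there were 2 + 3 = 5 subjects of 20 (25%); on placebo, 3 of 20 (15%), since each subject's other eye received placebo. The crude difference is 10 percentage points. Of the 18 events, 5 + 6 = 11 were on active drug, so at least 17 − 11 = 6 of the 17 events judged related were on placebo.

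US related ocular events: 8 subjects on 0.25%, 1 on placebo. Arm sizes are not given. If the three arms were equal (an assumption), this is 8/50 = 16% against 1/50 = 2%. Five subjects on 0.25% withdrew for allergic conjunctivitis, which 7.2.5 does not exclude, and the protocol does not say how many of them are among the 8. If all five are, and such cases would again be diagnosed, at most 8 − 5 = 3 of the 8 could have been lost under 7.2.5. If none are, the ceiling is 8. Neither figure estimates the loss in this trial.

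**The case against.** The strongest case against is that 7.2.5 is narrower than it first looks. Bullet 1 begins with fluctuation of the disease, and a drug-induced reaction is not fluctuation. Bullet 2 excludes a scale result and keeps it as a safety endpoint. It does not stop a site from recording pain that a subject reports, and an AE query follows the tolerance assessment at Visit 2. AE queries occur at every visit, subjects are told to report AEs between visits, and concomitant ocular medications are summarized, so a reaction that needed treatment would leave a trace.

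Most of this stands, and it rules out stronger readings that a reader might infer:

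- *That 7.2.5 bars every known reaction to this drug from the AE tables.* It does not. Allergic conjunctivitis is a separate diagnosis, and pain after later doses falls outside bullet 2.
- *That a quarter of the active arm, about 12 of 50, would have unrecorded hyperemia.* That carries over the Phase I rate of 5 of 20 and ignores the 3 subjects with hyperemia on placebo. The rate pools 0.5 and 5 mg/mL, neither of which is this trial's 2.5 mg/mL, in healthy subjects dosed for one day. All the hyperemia was mild.
- *That the ocular comparison is biased.* The documents show that it could be, not that it is.

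The objection does not remove the unqualified second sentence of bullet 1, the lack of any limit in bullet 2, or the silence on whether 7.2.1 or 7.2.5 governs. Bullet 3 shows that the authors knew how to write such a limit.

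**Conclusion.** The point holds as an unresolved conflict between Protocol 7.2.1 and 7.2.5. Worsening redness, burning or itching, and pain at the first dose, may be under-recorded as AEs, and sites may differ in how they record them. Slit-lamp results, the tolerance summary and withdrawal reasons reduce the gap but do not close it.

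The size cannot be derived from the documents, because it depends on how sites read 7.2.5. The earlier counts show only that local reactions of this kind were reported. The US percentages by arm rest on an assumed 50 per arm.

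The missing analysis of the timed tolerance scale is a smaller, related gap. Protocol 9.5.2 already calls for drop tolerance to be summarized, and the table shells, which are a separate document, may include the scale. The SAP text does not.

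**What to change.** Reconcile Protocol 7.2.1 and 7.2.5 by extending the exception in the CAE bullet to bullets 1 and 2. Record an AE when a dry-eye sign or symptom or a drop-tolerance result:

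- exceeds the expected range of dry eye relative to the subject's Visit 2 baseline; or
- is suspected by the investigator to be due to the study drug; or
- leads to treatment, interruption or withdrawal.

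These triggers parallel those that Protocol 7.2.6 already sets for laboratory abnormalities. The protocol does not define the expected range, and a first-dose tolerance score has no earlier value for comparison, so the second and third triggers are needed as well as the first.

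Do not add a list of findings that are always recorded when new or worsened. Redness is scored in half-grade steps in subjects who all enter with some, so such a list would turn any half-grade rise into an AE.

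In SAP 7.2, add a summary by arm of the drop-tolerance scale immediately after the first dose and at 1 and 2 minutes, in line with Protocol 9.5.2.

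The cost is a short protocol amendment, one more table, and some additional AE records in both arms, including some dry-eye worsening on placebo. Treatment and visits do not change.
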